28MAY2014

NCT02416934

Unique Protocol ID: 1405296745

Brief Title: Dysphagia Following Anterior Cervical Spine Surgery; Steroid vs Saline (DysDexVSSal)

Title: The Effects of Perioperative Steroids on Dysphagia Following Anterior Cervical Spine Surgery: A Randomized, Prospective, Double-Blind Study

The Effects of Perioperative Steroids on Dysphagia Following Anterior Cervical Spine Surgery: A Randomized, Prospective, Double-Blind Study

This prospective, randomized, double blind, controlled study evaluates the effect of perioperative IV steroids versus saline on swallowing after anterior cervical spine surgery. The specific aim of this study is to determine if perioperative steroids can positively influence post-operative swallowing following anterior cervical surgery.

Literature Review

Anterior approaches to the cervical spine were developed in the late 1950s and have been a mainstay of operative treatment for cervical disorders. The most common etiology of cervical spine problems requiring surgery is degenerative in nature; however, traumatic, neoplastic, infectious, and deformity-based conditions that require surgery are often approached anteriorly as well. The common types of procedures include anterior cervical discectomy and fusion (ACDF) at one or more levels, anterior cervical corpectomy and strut grafting at one or more levels, hybrid reconstruction following corpectomy plus ACDF, and more recently, total disc arthroplasty. All of these procedures utilize the same operative dissection to expose the anterior cervical spine. They also all require retraction of the esophagus often for several hours in the more complex cases.

Dysphagia is the term for symptomatic swallowing difficulties in patients. Swallowing is known to be a complex neuromuscular function with innervation from the pharyngeal plexus, the ansacervicalis, and cranial nerves IX, X, and XII. Virtually all patients will have some swallowing difficulty immediately after an anterior cervical spine procedure (1). The primary cause of this dysphagia is not believed to be denervation from the surgical approach but rather edema and late fibrosis in the esophageal tissue from the pressure of retractors (2,3). This has been shown histologically in a sheep study done by Cavusoglu et al (4). Other factors contributing to postoperative dysphagia include the presence of an anterior plate, the number of operative levels, higher levels of the cervical spine (such as C3-C4), duration of surgery, hematoma, and female gender (5-8).

Despite the anterior approach for cervical surgery having been popular for decades, it is only in the last several years that better studies have clarified the problem. In 2002, Bazaz et al. documented higher percentages of dysphagia months after surgery than had previously been known (9). These investigators obtained patient-reported symptoms at various time points up to one year following anterior cervical surgery. They developed a scale of none, mild, moderate, and severe symptoms of dysphagia and reported on 249 patients. The incidence of symptomatic swallowing difficulty was a surprising 50% at one month, 32% at two months, 18% at six months, and 12.5% at 12 months. Moderate to severe symptoms were still noted in 4.8% of patients six months post-operatively. Similarly, Riley et al. published on a large Cervical Spine Research Society cohort of 534 patients. Their data also showed a substantial percentage of symptoms three months post-operatively (29%). Six percent of patients still had some dysphagia 24 months post-operatively (10).

Steroids have long been used clinically for their physiologic effect of decreasing soft tissue edema. This effect has been utilized commonly in patients with spinal cord injury, cerebral swelling, and various pulmonary conditions. Some studies suggest a decrease in upper airway edema following cervical spine surgery, (11) though a randomized controlled trial done by Emery et al. found no benefit from steroids in the multi-level corpectomy patient population (12). Lee et al did a randomized study regarding intraoperative steroid soaked collagen sponges and their effect on prevertebral soft tissue swelling (13). The measurable soft tissue edema was decreased in the early time periods in the steroid group, and lower VAS (visual analog scale) scores regarding odynophagia were documented in the steroid group as well. Our study will use intravenous steroids and use two established dysphagia questionnaires for a more focused, in depth investigation of post-operative swallowing symptoms.

Steroids can cause hyperglycemia in predisposed patients such as diabetics and chronic use can suppress the immune system. High doses for longer periods of time can also result in avascular necrosis of the femoral head. In very short treatment periods such as a few days, the safety profile for steroid use is extremely high and indeed remains a common treatment option in spine patients as well as in many other disciplines. If steroids are beneficial in this clinical setting, it could lead to greater patient satisfaction, decreased hospital length of stay, and perhaps avoid permanent symptoms of dysphagia. If steroids are of no benefit than decreased peri-operative use could result in cost savings and avoid potential complications of the drug.

1. Riley LH 3rd, Vaccaro AR, Dettori JR, et al. Postoperative dysphagia in anterior cervical spine surgery. *Spine* 2010;35(9 Suppl):S76-85.

This investigation is a prospective, randomized, double-blind, controlled trial testing peri-operative steroids versus saline and the effect on swallowing after anterior cervical spine surgery. Persons between the ages of 18 and 80 undergoing anterior cervical decompression and stabilization procedures for degenerative conditions are eligible for the study. This would include persons undergoing anterior cervical discectomy and fusion (ACDF), hybrid constructs, corpectomy(ies), and disc arthroplasty. Persons excluded from the study include those with major trauma, neoplastic, or infectious conditions requiring surgery. Also excluded are persons undergoing anterior-posterior operations, those with a history of previous anterior cervical spine surgery, any one requiring a halo vest, persons on chronic steroids, and persons remaining intubated postoperatively.

Swallowing symptoms will be measured using the patient reported Bazaz scale and the Dysphagia Short Questionnaire. Swallowing data will be obtained pre-operatively, one day and two days post-operatively and then one week, two weeks, four weeks, three months, six months, and one year post-operatively. Other data to be collected for analysis includes patient comorbidities, levels and type of surgery, intra-operative fluids, estimated blood loss, type of retractors, type of brace if any, length of stay, and other surgically related complications. Patient clinical outcomes will be captured using our web-based progress reports.

Participants in this study will complete the QoL-12, Neck Disability Index, and Visual Analog Scale questionnaires electronically pre-operatively and at one month, three months, six months, and one-year post-operative time points. This outcome data will help us analyze the swallowing function or symptoms with the overall clinical course of the participants enrolled in this study.

Inclusion Criteria:

- Elective anterior approach to subaxial cervical spine (C3 - T1)
- Ages 18-80

Exclusion Criteria

- Traumatic or tumor etiologies
- undergoing anterior-posterior operations
- neoplastic, or infectious conditions requiring surgery
- a history of previous anterior cervical spine surgery
- any patient requiring a halo vest
- patients on chronic steroids
- patients remaining intubated post-operatively (please see more under risks below)
- less than 18 years of age
- pregnant women
- no phone

Procedures

Persons who have chosen to undergo anterior cervical spine surgery will be seen at the clinic for a pre-operative visit. The surgeons on the protocol will discuss the study and the subjects will be given the opportunity to participate. If the subjects agree to participate, a consent form will be administered by a member of the research team. The Bazaz and Dysphagia Short Questionnaire will be administered to subjects at this visit prior to surgery and again at Day 1, Day 2, 1 week, 2 weeks, 1 month, 3 months, 6 months, and 12 months after surgery. If the subject does not come for a clinic visit at the follow up times, he/she will be called to answer the questions on the surveys. The windows-of-time in which subjects may be called after discharge include: for follow up for week 1 and week 2, two days before or after the actual day of 1 or 2 weeks; for week 4, three days before or after the actual day of 4 weeks; for 3 months and 6 months, a week before or after the actual date of 3 or 6 months; for 1 year, 2 weeks before or after the actual date of 1 year. Subjects will be randomized to either the steroid administration group or the saline administration group. Subjects randomized to the experimental (steroid) group will receive 0.3 mg/kg of intravenous dexamethasone within one hour of the incision, then 0.15 mg/kg every eight hours (window of time 45 minutes on both ends of the eight hour time, e.g. if the time is 8 pm, the dose could be given from 7:15 pm through 8:45 pm) for two doses. This dosage is approximately 20 mg, 10 mg, and 10 mg of dexamethasone. Subjects in the control (saline) group will receive a similar volume of saline on the same schedule for three doses. This is a double-blind trial; the surgeon (and anesthesiologist) and the subject will not know what group assignment the subject has received. The in-patient pharmacy will generate IV bags that are labeled for the study but that are blinded as to medication/saline labels. Randomization will be performed by the satellite pharmacist outside of the operating room. This person will also supply the study drug.

Sample Size

70

Sample Size justification

Our power analysis indicates 64 subjects with 32 in each arm is enough to give us 81% power to reject the null hypothesis. We are adding an additional 10% to that number as we expect to have a loss to follow up of approximately 10%.

Data Analysis

Power and sample size calculations are based on the presence or absence of dysphasia at 2-weeks. Based on a literature review we postulated that 50% of the subjects in the control arm would experience mild, moderate or severe dysphasia. If that figure can be improved to the point where just 20% of the subjects are similarly affected, then that, in our opinion, would represent clinical success. Under the above scenario, 32 subjects in each arm would give us 81% power to reject the null hypothesis. We plan to analyze the data in two ways. First, we will look at the time-to-event where the event is "no dysphasia" in a discrete time survival model. Second, we will use a repeated measures ordinal categorical model to assess the effect of steroid/control in a generalized linear model. We have an electronic database that we will use to track patient outcomes. If subjects are unable to return to clinic, they will be able to complete the database questionnaires online. Our clinical research coordinator will also be able to contact subjects via phone to complete the Bazaz scale and Dysphagia Short Questionnaire.

Potential Risks/Discomforts/Privacy

Completion of the Bazaz scale and Dysphagia Short Questionnaire may cause some discomfort. The only expected side effect, in the group receiving steroids, would be possible elevation of serum glucose levels in diabetic subjects. The serum glucose levels in diabetic subjects will be monitored postoperatively with routine postoperative laboratory testing. All other procedures are standard of care.

Potential subjects will be recruited/consented for the study in private rooms at the Physician Office Center (POC) when they come for their History and Physical visit prior to surgery. All HIPAA safeguards are in place at the POC. Subjects will not be contacted outside of what is necessary for the research study.

Potential Benefits

To Subject: The group randomized to steroid administration may experience less or no dysphasia two weeks after the surgery.

To Society: The benefit to society will be publishing the results of the study regardless of whether we see improvement in dysphasia after administration of steroids or no improvement. Other surgeons performing this type of surgery will benefit knowing our results.

Risk to benefit ratio: The benefit of knowing whether administration of steroids causes less dysphasia in anterior cervical spine surgery as opposed to saline administration, outweighs the risk/discomfort of completion of surveys measuring the prevalence and

severity of dysphagia and the possibility of hyperglycemia in patients with diabetes who will be routinely monitored and treated during surgery and the course of their hospital stay.

Consent Procedures

Potential subjects who have chosen to undergo anterior cervical spine surgery will be seen at the clinic for their History and Physical visit. The surgeons on the protocol will discuss the study and the subjects will be given the opportunity to participate. If the subjects agree to participate, a consent form will be administered by a member of the research team signed by the subject and research team member and a copy of the signed consent form will be given to the subject. The Bazaz survey and the Dysphagia Short Questionnaire will be administered to subjects at this History and Physical visit prior to surgery and again at Day 1, Day 2, week 1, week 2, months 1, 3, 6, and 12 after surgery. Subjects will be randomized to either the steroid administration group or the group receiving saline. Subjects will undergo anterior cervical spine surgery per standard of care.

Confidentiality

Subjects will be recruited/consented in private rooms of the POC. The Bazaz scale and Dysphagia Short Questionnaire will have assigned numbers attached to the outcome tools instead of any identifying information from the subject. Scores from the electronic tools used to gather Health Progress Report (outcomes) data will be placed in the excel spreadsheet with the assigned number. The number, corresponding to the patient, will be kept on a password protected computer on an excel spread sheet. The surveys will be kept in a locked file cabinet, in a locked room when the research team members are not present, in the department of Orthopaedics, third floor health sciences. All HIPAA safeguards are in place.

No cost and no payment to subjects

No radioactive materials will be used and there will be no exposure to infectious agents.

No advertisements will be used to promote the study.

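### Remaining intubated after surgery is an exclusion criterion, but it can be known only after randomisation and the first dose

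*Protocol*

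**What the plan says.** The Exclusion Criteria list in the protocol contains "patients remaining intubated post-operatively (please see more under risks below"). The prose of Research Design carries the same rule, excluding "persons on chronic steroids, and persons remaining intubated postoperatively".

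Under Procedures, consent is taken at the pre-operative visit. Then "Randomization will be performed by the satellite pharmacist outside of the operating room", and the same pharmacist supplies the study drug. Steroid patients "will receive 0.3 mg/kg of intravenous dexamethasone within one hour of the incision", and the saline arm follows the same schedule.

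The Literature Review reports mixed evidence on the airway. "Some studies suggest a decrease in upper airway edema following cervical spine surgery", but one randomised trial "found no benefit from steroids in the multi-level corpectomy patient population".

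The exclusion list refers the reader to the risk text for more. Under Potential Risks/Discomforts/Privacy that text covers questionnaire discomfort and glucose: "The only expected side effect, in the group receiving steroids, would be possible elevation of serum glucose levels in diabetic subjects". Neither that section nor the risk-to-benefit paragraph mentions intubation.

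**The concern.** An exclusion criterion should rest on facts available before allocation. This one rests on something that happens after allocation and after the first dose, and that the study drug might influence. The protocol attributes post-operative dysphagia mainly to edema and late fibrosis from retractor pressure. If edema also prolongs intubation, removing these patients selects on something related to both treatment and outcome.

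There are two possibilities:

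- **Steroids affect who stays intubated.** The patients removed then differ between arms, and randomisation no longer protects the comparison.
- **Steroids do not affect it.** The comparison stays valid apart from chance imbalance, but it applies to a narrower population than the one randomised.

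Once these patients have left the study, a reader cannot tell which case applies unless intubation is reported by arm.

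**Working it through.** **Order of events**

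1. Consent is given at the pre-operative clinic visit (Procedures).
2. The pharmacist randomises and supplies the blinded bags (Procedures). No clock time is given, but this must precede the first dose.
3. The first dose is given within one hour of the incision (Procedures). Even if that allows a dose shortly after the incision, surgery is still under way.
4. Surgery ends, and only then is it known whether the patient remains intubated.

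The criterion depends on step 4. It cannot be applied before step 2.

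**Inputs for the size**

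- From the protocol: 70 patients in two equal arms, so 35 per arm; dysphagia at two weeks of 50% (control) and 20% (steroid).
- Assumed: a two-sided 5% pooled z-test at week 2 (the protocol states neither alpha nor sidedness), no other losses, and all counts of excluded patients, since no intubation rate is given.

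**The protocol's own figure.** Power is

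Φ{[(p1 − p2) − z·√(p̄(1 − p̄)(1/n1 + 1/n2))] / √(p1(1 − p1)/n1 + p2(1 − p2)/n2)}

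where p̄ is the pooled rate. With 32 per arm, 50% versus 20% and z = 1.645 (one-sided 5%): (0.30 − 1.645 × 0.1192)/0.1132 gives 82.1%, close to the stated 81%. With z = 1.96 (two-sided 5%) it gives 72.1%. That gap is a separate matter. It explains why the two-sided baseline below is not 81%.

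**Baseline, 35 per arm.** (0.30 − 1.96 × 0.1140)/0.1082 = 0.707, so power is 76.0%.

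**Every excluded patient assumed dysphagic at week 2.** The rate left in an arm after k exclusions is (35p − k)/(35 − k). For example, three controls: (17.5 − 3)/32 = 45.3%; two steroid patients: (7 − 2)/33 = 15.2%.

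| Excluded, control / steroid | Control rate | Steroid rate | Difference (points) | Power |
|---|---|---|---|---|
| 0 / 0 | 50.0% | 20.0% | 30.0 | 76.0% |
| 1 / 0 | 48.5% | 20.0% | 28.5 | 71.4% |
| 2 / 0 | 47.0% | 20.0% | 27.0 | 66.2% |
| 3 / 0 | 45.3% | 20.0% | 25.3 | 60.4% |
| 2 / 2 | 47.0% | 15.2% | 31.8 | 81.3% |
| 3 / 3 | 45.3% | 12.5% | 32.8 | 84.2% |
| 0 / 2 | 50.0% | 15.2% | 34.8 | 88.2% |

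Power above the baseline is not a gain. It reflects a difference inflated by selection.

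**Excluded patients no different from other controls.** Removing three controls at the 50% rate leaves 32 versus 35 patients and a 30-point difference; power is 74.2%. Only numbers are lost.

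**No true effect at week 2 (50% in both arms).** Removing three dysphagic controls leaves 45.3% versus 50%, an apparent 4.7 points against steroid produced by the exclusion alone.

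**The case against.** Six points can be made in defence.

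- **Removal from the analysis is not stated.** The protocol calls these patients excluded but does not say that they lose follow-up, are replaced or leave the analysis. A SAP that is not shown may define the analysis set. This stands as a limit on certainty about the consequence. It does not rescue the criterion: no SAP can make it assessable before randomisation, and leaving the study is the plain reading of excluded.
- **Planned ventilation may be meant.** That could be known beforehand, but the wording is not limited to it.
- **Blinding.** Surgeon, anesthesiologist and patient do not know the arm, so nobody can select knowingly by arm. This stands and narrows the concern: systematic bias needs a real drug effect on intubation. The protocol treats an effect on the airway as unsettled.
- **The illustration is not the planned analysis.** The protocol plans a discrete-time survival model and a repeated-measures ordinal model; week 2 is only the sizing basis. Most scenarios also take the extreme case that all excluded patients are dysphagic. Both points are fair. The figures show direction and sensitivity, not a forecast, and the number excluded could be zero.
- **Intubated patients cannot answer questionnaires.** That affects Day 1 and Day 2. Week 2 and later visits can still be collected, by phone if needed.
- **The cross-reference is editorial.** Agreed; it adds nothing to the bias argument. It does mean that the one place meant to explain the criterion is silent.

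**Conclusion.** The concern holds. The protocol fixes an eligibility rule on an event that follows randomisation and the first dose and that the study drug might affect. The timing is certain from the protocol's own sequence.

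The size is not certain. Under the assumptions above, two or three exclusions in a trial of 70 move the week-2 difference from 30 points to anywhere between 25.3 and 34.8, and power from 76% to between 60% and 88%. If the excluded patients resemble the other controls, or if none occur, the effect is small or nil. The 10% allowance in the sample size is for loss to follow-up and does not provide for these exclusions. The point should be fixed: the defect is clear and the repair is cheap, although no actual bias has been shown.

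**What to change.** - Restrict the exclusion criteria to facts known before randomisation. If planned post-operative intubation was meant, say so.
- State that every randomised patient stays in the assigned group, is followed at all later visits including week 2, and is analysed as assigned.
- Report post-operative intubation by arm.
- Repair or delete the reference to the risk text.
- Secondary, and suitable for the SAP: fix in advance whether Day 1 and Day 2 scores in a patient still intubated are missing or set to the worst Bazaz category. The week-2 score itself is unaffected, but both planned models could use the early visits, so the choice may affect their estimates.

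Whether study dosing continues in such patients is for the sponsor to decide.

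The cost is the wording of one criterion, one statement on who is followed and analysed, and one cross-reference. The downside is that a few Day 1 and Day 2 scores will be missing or assigned by rule instead of reported by the patient.

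### The loss allowance adds 10% to the 64 subjects needed instead of dividing by 0.90, so 70 enrolled leaves 63 evaluable if a full 10% are lost by 2 weeks

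*Protocol*

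**What the plan says.** Under Sample Size, the protocol gives 70. Under Sample Size justification it states: "Our power analysis indicates 64 subjects with 32 in each arm is enough to give us 81% power to reject the null hypothesis". It then explains the step from 64 to 70: "We are adding an additional 10% to that number as we expect to have a loss to follow up of approximately 10" per cent.

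The Data Analysis section gives the basis of the power figure. The endpoint is binary and early: "Power and sample size calculations are based on the presence or absence of dysphasia at 2-weeks". The control assumption is that "50% of the subjects in the control arm would experience mild, moderate or severe dysphasia", and success is that figure "improved to the point where just 20% of the subjects are similarly affected". The section then repeats the claim: "Under the above scenario, 32 subjects in each arm would give us 81% power to reject the null hypothesis".

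Neither section states the alpha, the sidedness or the test. Neither says by which visit the 10% loss is expected. No other allowance for loss appears in the protocol.

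**The concern.** The added 10% has one purpose: to leave 64 evaluable subjects after the expected loss. A loss rate describes the share of enrolled subjects who drop out, so the number needed has to be divided by the share who stay. Adding 10% to the number needed always falls a little short, because 10% of the larger enrolled number is more than was added. Rounding 70.4 down to 70 widens the gap slightly.

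At stake is whether the enrolment figure delivers the evaluable size to which the 81% is tied. If it does not, the justification should say what it does deliver.

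**Working it through.** **Inputs.** Evaluable number 64, 32 per arm; enrolment 70; loss about 10% (Sample Size and Sample Size justification). Control rate 50%, steroid rate 20%, stated power 81% at 32 per arm (Data Analysis). Alpha and sidedness are not given, so 0.05 one-sided and 0.05 two-sided are both assumed below.

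**1. The plan's enrolment figure.** 64 × 1.10 = 70.4, printed as 70. This reproduces the target and confirms that the 10% was applied to the number needed.

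**2. What 70 leaves at exactly 10% loss.** 70 × 0.90 = 63, or 31.5 per arm on average (31 in one arm and 32 in the other).

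**3. The loss that 70 can absorb.** 70 − 64 = 6 subjects; 6/70 = 8.6%.

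**4. The matching inflation.** 64/0.90 = 71.1. Enrolling 71 leaves 71 × 0.90 = 63.9, still just short, so rounding alone does not explain the gap. For equal arms the match is 72, since 72 × 0.90 = 64.8.

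**5. Chance variation around 10%.** If each subject is lost independently with probability 0.10, the binomial probabilities are:

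| Enrolled | At least 64 evaluable | Both arms at least 32 |
|---|---|---|
| 70 (35 + 35) | 44% | 28% |
| 72 (36 + 36) | 71% | 51% |

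These figures treat 64 and 32 as hard thresholds. Step 6 shows that power does not behave that way.

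**6. Effect on power.** Pooled normal approximation for 0.50 versus 0.20:

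power = Φ{[0.30 − z·√(p̄(1 − p̄)(1/n₁ + 1/n₂))] / √(0.25/n₁ + 0.16/n₂)}, where p̄ is the pooled rate (0.35 with equal arms).

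At 32 per arm the two square roots are √(0.35 × 0.65 × 2/32) = 0.1192 and √(0.41/32) = 0.1132.

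- One-sided 0.05 (z = 1.645): (0.30 − 0.1961)/0.1132 = 0.918, power 82.1%.
- Two-sided 0.05 (z = 1.960): (0.30 − 0.2337)/0.1132 = 0.586, power 72.1%.

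| Evaluable | One-sided 0.05 | Two-sided 0.05 |
|---|---|---|
| 32 + 32 (64) | 82.1% | 72.1% |
| 32 + 31 (63) | about 81.5% | 71.3 to 71.5% |
| 31 + 31 (62) | 80.9% | 70.7% |

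The range at 63 depends on which arm is one short. Going from 64 to 63 costs about 0.6 points one-sided and 0.6 to 0.8 points two-sided. Exact enumeration of the two-sided chi-square test gives 73.4% at 64 and 72.9% at 63, a drop of 0.5. Exact power also moves in small jumps: the one-sided chi-square enumeration is slightly higher at 63 (82.7 to 83.2%) than at 64 (82.1%), which shows how little one subject matters.

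**7. Which basis reproduces 81%.** At one-sided 0.05, 82.1% is close to the stated figure, and the smallest equal arm size giving 81% is 32. At two-sided 0.05, the methods tried for 32 per arm give 62.2% (continuity-corrected), 64.4% (Fisher exact), 72.1% (pooled), 73.0% (arcsine), 73.4% (chi-square by enumeration) and 75.5% (unpooled). None is near 81%.

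**The case against.** Four points can be made for the plan.

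- **The loss is only approximate.** The protocol says about 10%, and a break-even of 8.6% could fairly be described that way. At 9% loss, 70 × 0.91 = 63.7, which rounds to 64. This stands: the shortfall is conditional on a full 10%.
- **The timing of the loss is not stated.** Sizing uses the 2-week endpoint while follow-up runs to one year. The protocol also provides telephone and online completion and excludes people without a phone. If 10% describes one-year loss, fewer would be lost by 2 weeks and 70 could leave 64 or more. This also stands. Against it, the protocol applies its single loss figure to the 2-week sample size and gives no separate figure for that visit.
- **The stated power survives.** A reader might infer that the trial misses its 81% because of this step. The documents do not support that. On the one-sided 0.05 basis that reproduces the figure, 63 evaluable subjects still give about 81.5%. On a two-sided 0.05 basis, 81% is not reached at 64 either. That gap of about 9 points (81 − 72.1) is a separate question, which enrolling 72 would not answer.
- **The probabilities look worse than the consequence.** A 44% chance of keeping 64 sounds serious, but having 63 costs less than one point of power, and even with 72 enrolled both arms reach 32 only about half the time. This is fair, and those figures should not be read as a measure of harm.

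What remains is that the enrolment figure and its method are both printed in the protocol, and at the loss rate it uses the method does not return the number it starts from.

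**Conclusion.** The inflation step is wrong as written, and the consequence is minor. If loss by 2 weeks is a full 10%, 70 enrolled leaves 63 evaluable, one fewer than the 64 intended; 70 keeps 64 only up to 6 losses, or 8.6%. The subject counts need no assumption about test, alpha or sidedness, only that the 10% applies to enrolled subjects by the sizing endpoint.

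The cost is about 0.5 to 0.8 points of power, assuming 50% versus 20% and alpha 0.05, one- or two-sided. This does not show that the trial is underpowered, and it does not show that 70 is an inadequate target.

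**What to change.** Restate the Sample Size justification along these lines: 70 enrolled allows for up to 6 losses (8.6%) by 2 weeks; at 10% loss about 63 subjects are evaluable, 31 or 32 per arm. Quote the power for 63, and state the alpha and sidedness used.

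This costs one or two sentences. The quoted power becomes about 0.5 to 0.8 points less favourable than the value for 64 on the same basis. No extra enrolment is required. If the sponsor prefers to keep 64 evaluable at 10% loss, the arithmetic match is 72, two more subjects, but the point does not depend on that choice.

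### The 81% power is calculated for any versus no dysphagia at 2 weeks, but the two planned analyses are different, neither is primary, and no alpha or sidedness is stated

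*Protocol*

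**What the plan says.** All of this is in the protocol. The Data Analysis section opens with the sizing basis: "Power and sample size calculations are based on the presence or absence of dysphasia at 2-weeks". The control assumption follows: "Based on a literature review we postulated that 50% of the subjects in the control arm would experience mild, moderate or severe dysphasia". The target is that "just 20% of the subjects are similarly affected, then that, in our opinion, would represent clinical success". The result is that "Under the above scenario, 32 subjects in each arm would give us 81% power to reject the null hypothesis". The Sample Size justification section repeats the figure: "Our power analysis indicates 64 subjects with 32 in each arm is enough to give us 81% power to reject the null hypothesis". Neither section gives a significance level or says whether the test is one- or two-sided, and no other section does.

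The same Data Analysis paragraph then states: "We plan to analyze the data in two ways". The first: "First, we will look at the time-to-event where the event is" freedom from dysphagia, in a discrete-time survival model. The second: "we will use a repeated measures ordinal categorical model to assess the effect of steroid/control in a generalized linear model". Neither is called primary, and no 2-week comparison or 2-week contrast is mentioned. Research Design lists eight post-operative swallowing assessments, from day 1 to one year; 2 weeks is one of them.

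**The concern.** A power figure belongs to a particular test of a particular outcome at a particular alpha. Here the outcome is given, but the analyses planned are of other quantities and the alpha is missing.

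The three quantities differ. The 2-week comparison asks what share of patients have any symptoms at one visit. The survival model asks when patients first become symptom-free: two patients who recover at day 2 and at week 2 differ in it, yet count alike in the 2-week comparison if both are symptom-free at that visit. The ordinal model separates mild from severe symptoms and draws on the repeated visits. Either model could reach significance without a 2-week difference, or miss one that exists.

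Two things are at stake. First, a reader cannot tell which result decides the trial; with two co-equal analyses there are two chances to claim success and no stated control of the overall error. Second, a reader cannot tell what risk of a false positive was accepted to obtain 81%.

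**Working it through.** **Inputs.** From the Data Analysis section: p1 = 0.50 (saline), p2 = 0.20 (steroid), n = 32 per arm, stated power 81%. Alpha and sidedness are not stated, so 5% is assumed and both sidedness options are shown.

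**Formula (pooled z).** Power = Φ[(d − z·SE0)/SE1], with
- d = 0.50 − 0.20 = 0.30
- SE0 = √(2 × 0.35 × 0.65 / 32) = 0.1192, using the mean rate 0.35
- SE1 = √((0.25 + 0.16)/32) = 0.1132

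**Reproducing the stated figure, one-sided 5% (z = 1.645).** (0.30 − 1.645 × 0.1192)/0.1132 = 0.918, so power = 82.1%. In reverse, the n for 81% power (z = 0.878) is [1.645 × √0.455 + 0.878 × √0.41]² / 0.30² = 31.05, rounded up to 32 per arm. That matches the protocol.

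**The same design at two-sided 5% (z = 1.960).** (0.30 − 1.960 × 0.1192)/0.1132 = 0.586, so power = 72.1%. The n for 81% would be [1.960 × √0.455 + 0.878 × √0.41]² / 0.30² = 39.4, or 40 per arm.

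**Other methods at 32 per arm.** The unpooled z replaces SE0 by SE1; the exact figures sum the binomial probabilities of all tables that reject.

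| Method | One-sided 5% | Two-sided 5% |
|---|---|---|
| Pooled z | 82.1% | 72.1% |
| Exact power, Pearson test | 82.1% | 73.4% |
| Arcsine | 82.4% | 73.0% |
| Unpooled z | 84.3% | 75.5% |
| Fisher's exact test | 74.8% | 64.4% |

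None of these reaches 81% at two-sided 5%. At one-sided 5% (the same as two-sided 10%) three of them come within 1.5 points of it.

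**Two co-equal analyses.** If each were tested at 5% and the two were independent, the chance of at least one false positive would be 1 − 0.95² = 9.75%. Both models use the same patients' swallowing data, so the tests should be positively correlated and the inflation smaller; the protocol does not allow its exact size to be calculated.

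**Power of the two planned models.** This cannot be computed. It depends on visit-by-visit symptom rates and on correlation within patients, and the protocol gives neither.

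**The case against.** The strongest reply is that a SAP may fill these gaps, that sizing on a simple binary outcome and analysing longitudinally is accepted practice, and that 2 weeks is a scheduled visit, so a 2-week contrast could be taken from the ordinal model. Part of this stands: model details may be left to a SAP, and such a contrast is feasible. But the protocol itself quotes a power figure for one test and then commits to two others without ranking them. Reading the order of the two analyses as a ranking does not help, because the first is the survival model, which the trial was not sized on.

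A reader might also infer more than the text supports:

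- *The 81% is wrong and the trial is underpowered.* Not shown. The figure fits one-sided 5%, and the stated aim is directional (a positive influence on swallowing). The shortfall exists only if two-sided 5% is intended. Solving backwards for an exact alpha would mean little, since the test method is also unstated.
- *The planned models have less than 81% power.* Not shown either; it could be higher or lower.
- *The protocol sets a success criterion and gives it no test.* The 50% to 20% sentence justifies an effect size; it is not a decision rule. Rejecting equality at 2 weeks would not itself prove a 30-point reduction.
- *The sizing outcome has no instrument.* This is thin. The none, mild, moderate and severe grades are those of the Bazaz scale as the Literature Review describes it.

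**Conclusion.** The point holds as a mismatch within the protocol. The 81% belongs to a 2-week two-group comparison that is not among the stated analyses, the two analyses that are stated carry no priority, and overall type I error is uncontrolled as written. The power figure cannot be interpreted without its alpha: the same 32 per arm gives about 82% at one-sided 5% and about 72-73% at two-sided 5% by pooled z or exact Pearson test, a gap of about 9 to 10 points. Under the two-sided reading, the chance of missing the assumed effect would be about 27-28% rather than the stated 19%. These figures rest on the protocol's own rates and on 32 evaluable patients per arm; the two-sided ones are conditional on an alpha that the protocol does not state. This should be fixed, but it does not show that the trial is too small.

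**What to change.** In the Data Analysis section:

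1. Name one primary analysis. The simplest, because it matches the sizing, is any (mild, moderate or severe) versus none on the Bazaz scale at 2 weeks, steroid against saline. It can be a two-group comparison of proportions, or the 2-week contrast from the planned repeated-measures model with a treatment-by-visit term.
2. Label the survival model and the all-visit ordinal effect secondary.
3. State alpha and sidedness.
4. Restate the power at 32 per arm for that test: about 72-73% at two-sided 5%, or about 82% only at one-sided 5%. Make the same change in the Sample Size justification section.

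If the sponsor prefers one of the two longitudinal models as primary, the power must be restated for that model, which needs visit-by-visit assumptions that the protocol does not contain.

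The cost is wording only, with no new data and no added enrolment. The downsides are a less favourable stated power if two-sided 5% is chosen, and giving up a claim of success based on a longitudinal model alone.
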